6.9. Procedures for unmasking treatment assignment

Treatment assignments are double masked throughout the study until after all data collection for the TONIC trial has been completed (ie, after completion of the 24 week post trial follow-up for all patients). Every effort will be made to maintain the masking throughout the study except in emergency situations. The code of specific study drug will not be broken without the knowledge of the clinical center's principal investigator.

Unmasking of study drug will occur under the following conditions:

- **Severe allergic reaction (Stevens-Johnson Syndrome):** Study drug is stopped indefinitely. The patient, primary care provider (PCP), and the investigator will be unmasked.
- **New onset diabetes and fasting blood glucose at least 140 mg/dL on two separate occasions:** Study drug will be stopped indefinitely. The patient will be referred to their PCP with standard American Diabetes Association recommendations. The patient and PCP will be unmasked to metformin assignment.
- **Pregnancy during the study:** Study drug will be stopped indefinitely, and the coded study drug will be unmasked. The patient and PCP will be notified of the assigned treatment and the associated risks of teratogenicity.
- **Development of hepatotoxicity:** Hepatotoxicity will be defined as the development of jaundice with a serum direct bilirubin of > 1.0 mg/dL or a doubling of the serum baseline ALT **and** ALT value > 400 U/L during treatment. There will be no unmasking until study conclusion and subjects will be advised to avoid metformin and vitamin E until the unmasking is done. One exception is if any of these subjects with hepatotoxicity develop diabetes during the study duration. In this situation, the study medication will be unmasked and subject and PCP will be notified.

In unforeseen situations where the clinical center principal investigator considers unmasking is in the best interest of the participant's health and well being, unmasking could be done after notifying and obtaining approval of the NASH CRN Executive Committee.

The Data and Safety Monitoring Board will review all instances of unmasking that occur. The Data and Safety Monitoring Board may develop its own set of unmasking guidelines for monitoring purposes.

TONIC Trial Protocol

7. Statistical design and analysis

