6.3. Safety issues related to placebo

As presented in the section above, it is anticipated that about 13 subjects in the placebo group will develop new-onset diabetes mellitus during their participation in the TONIC trial. Participants will be seen frequently during the study period for assessment of symptoms consistent with uncontrolled hyperglycemia and will have fasting glucose levels measured at 24, 48, 72, 96, and 120 weeks after randomization (at 48, 96, and 120 weeks this measurement is part of OGTT). Patients with fasting glucose ≥ 126 mg/dL will have the same test repeated within 6 weeks to confirm the diagnosis of new-onset diabetes. Patients with a diagnosis of new onset diabetes will be managed according to the following stepped care approach and the primary care physician will be notified.

- (a) Lifestyle counseling to reduce excess body weight and increase exercise
- (b) Education on diabetic diet
- (c) If fasting glucose remains greater than 140 mg/dL after three months or if patient develops symptomatic diabetes, treatment with sulfonylurea will be initiated.
- (d) If patient still is unable to maintain glycemic control, primary care physician may request unmasking of the study medication and should institute necessary measures for diabetes management. Study medication will not be unmasked to the investigator. These patients will be followed at scheduled intervals to collect other outcome data; however, they will

not have the OGTT scheduled for the visits at 48, 96, and 120 weeks but will have only fasting glucose levels measured.

During the trial, if a participant develops side effects thought to be due to the study drug and requires cessation of study drug, the medication will be stopped for 4 weeks. If the side effects disappear, an attempt will be made to reintroduce the study medication after 4 weeks. If the symptoms reappear, study medication will be once again stopped and the patient will no longer receive the study medication, but will be followed in the study according to the protocol, in keeping with the “intention-to-treat” paradigm.

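### Sections 6.9 and 6.3 conflict on when and how unmasking happens in new-onset diabetes, and sections 3.3 and 6.3 set different hold lengths for side effects

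*Supplement*

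**What the plan says.** **Diabetes, section 6.9.** The trigger is "New onset diabetes and fasting blood glucose at least 140 mg/dL on two separate occasions". The action is: "Study drug will be stopped indefinitely. The patient will be referred to their PCP with standard American Diabetes Association recommendations". It continues: "The patient and PCP will be unmasked to metformin assignment". The section presents its list as conditions under which unmasking will happen. It sets no waiting time and no earlier treatment step.

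**Diabetes, section 6.3.** A fasting glucose of 126 mg/dL or more is repeated within 6 weeks to confirm new-onset diabetes. Steps (a) and (b) are lifestyle and diet advice. Step (c) reads: "If fasting glucose remains greater than 140 mg/dL after three months or if patient develops symptomatic diabetes, treatment with sulfonylurea will be initiated". Step (d) reads: "If patient still is unable to maintain glycemic control, primary care physician may request unmasking of the study medication". It adds: "Study medication will not be unmasked to the investigator". None of the four steps says whether study drug continues or stops.

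**Side effects thought due to study drug that require cessation.** Section 3.3 stops drug for two weeks and then retries. If symptoms return, the study physician discusses termination with the Executive Committee. The last paragraph of 6.3 stops drug for four weeks and then retries. If symptoms return, drug ends for good and the patient is followed under intention to treat.

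The document history (10.6) lists no change that reconciles these sections.

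**The concern.** The general masking rule in 6.9 is "Treatment assignments are double masked throughout the study until after all data collection for the TONIC trial has been completed", so each exception needs one trigger that every center applies alike. For diabetes there are two. One requires unmasking at the second value of at least 140 mg/dL. The other allows it on request after stepped care has failed. A site following 6.3 could leave a family and PCP masked when 6.9 says they must be told. Section 6.2 sends readers to 6.3, not 6.9, for the diabetes management strategy, so a site may well start there.

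For side effects, a site cannot hold drug for both two weeks and four. The heading of 6.3 refers to placebo, but its text covers any participant, and masked sites cannot apply a rule by arm.

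At stake is uniform handling of masking and dosing in children. The primary test and its error rates are not touched.

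**Working it through.** **1. The diabetes rules side by side**

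| | 6.9 | 6.3(a)-(d) |
|---|---|---|
| Entry | New-onset diabetes, fasting glucose ≥140 mg/dL twice | Fasting glucose ≥126 mg/dL, confirmed by repeat within 6 weeks |
| Before unmasking | Nothing further | Lifestyle and diet; sulfonylurea if >140 mg/dL after three months or if symptomatic; then failure of control |
| Unmasking | Required | At the PCP's request |
| What is revealed | Metformin assignment | Study medication |
| Investigator | Not among those unmasked | Stays masked |
| Study drug | Stopped indefinitely | Not stated |

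A child who reaches step (c) by the glucose route has stayed above 140 mg/dL. On the natural reading there was one such value before the three-month check and another at it. Two values above 140 are two values of at least 140, so this child meets 6.9 no later than step (c). Step (d) comes after (c) and still treats the assignment as masked. The conflict for this child therefore needs no assumption about timing.

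**2. How long unmasking could be delayed**

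Inputs: scheduled fasting glucose at weeks 24, 48, 72, 96 and 120 (6.3); three months = 91.3/7 = 13.0 weeks. Assumption: the second value of at least 140 mg/dL comes 1-6 weeks after the first. Section 6.9 sets no interval, and the six-week repeat in 6.3 confirms diabetes at 126 mg/dL, not 140. Section 6.3 does not say when its three months start, so both starts are shown for a week 24 case without symptoms.

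- 6.9 trigger: 24 + 1 = week 25 to 24 + 6 = week 30.
- Step (c), three months from the first value: 24 + 13 = week 37. Delay to the sulfonylurea step: 37 − 30 = 7 to 37 − 25 = 12 weeks.
- Step (c), three months from the second value: 25 + 13 = week 38 to 30 + 13 = week 43. Delay: 13 weeks.
- Second value is the three-month check itself: both sections are triggered by the same test, so the delay to step (c) is 0.
- Symptomatic child: step (c) has no waiting period, so there may be no delay to that step.

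Unmasking under (d) follows (c) by an unstated time, or never happens if the PCP does not ask. The differences are the same for a case found at week 48 or 72.

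**3. How many children**

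The only related figure is the 13 expected diabetes cases in the placebo group (6.2), with vitamin E assumed the same. It reproduces: 60 × 2 years × 0.11 = 13.2. Over exactly 96 weeks (1.84 years) it is 60 × 1.84 × 0.11 = 12.1. The rate comes from adults and counts all new-onset diabetes. The number reaching 140 mg/dL twice is not given.

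**4. Side-effect hold**

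4 − 2 = 2 weeks, and 2/96 = 2.1% of the treatment period. On recurrence, 3.3 requires a discussion and leaves its result open, while 6.3 requires a permanent stop. A site can stop drug and hold the discussion, so only the hold length is strictly incompatible.

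**The case against.** The best defense is that 6.9 is the section on unmasking, uses mandatory language, and is the only text on stopping drug for diabetes, so a site would naturally follow it. Section 6.3(d) also has ground of its own: children diagnosed at 126 mg/dL or more, or symptomatic, who never have two values of at least 140. The scope differs too. After 6.9 reveals the metformin assignment, a PCP could still ask for the rest. Finally, "The Data and Safety Monitoring Board will review all instances of unmasking that occur".

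Much of this stands. It shows that the sections overlap in part and points to the sensible resolution. It does not remove the conflict, because 6.3(c) is itself set above 140 mg/dL, (d) makes unmasking optional and later, and neither section refers to the other. DSMB review comes after the event, and a child left masked under 6.3 produces no unmasking to review.

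A reader might infer more than the text allows:

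- **That 6.3 keeps the child on drug, so 6.9 costs a large share of treatment.** No sentence in 6.3 says so. A site could stop drug under 6.9 and still give stepped care.
- **That unmasking is delayed by at least 13 weeks.** That needs a start for the three months, and a date for the second value, that the protocol does not give.
- **That the recurrence rules are irreconcilable.** They differ in wording, but both can be followed.

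**Conclusion.** Two inconsistencies stand in the current protocol. The first is direct: 6.9 requires unmasking at two fasting values of at least 140 mg/dL, while 6.3 makes it optional and later for a child who normally already meets that trigger. The delay is not determined. It is roughly 7-13 weeks to the sulfonylurea step for a child without symptoms, if the second value comes 1-6 weeks after the first, and possibly none to that step otherwise. The difference on stopping drug is implied only.

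The second is a two-week versus four-week hold for the same kind of side effect, a difference of 2.1% of the treatment period.

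The number of children affected is unknown. It should not be read as the 13 expected diabetes cases per group. Nor do the documents support a claim of damage to the primary analysis: follow-up continues under intention to treat, the investigator stays masked in the diabetes pathway, the outcome is a laboratory value, and alpha, power and sample size do not change. The point should be fixed because these are operative safety and masking instructions and sites need one rule for each situation.

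**What to change.** - State in 6.9 that it governs stopping and unmasking once fasting glucose is at least 140 mg/dL on two occasions in new-onset diabetes.
- Limit the stepped care and PCP-request unmasking in 6.3 to children who do not meet 6.9, reword (c)-(d) to match, and cross-refer the two sections.
- Keep one hold length and one recurrence rule in 3.3. Delete the duplicate in 6.3, but keep its sentence on intention-to-treat follow-up.
- Have the clinical leads and the DSMB confirm the rules, and send all centers one memo.

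The cost is a protocol clarification and the memo. No tests are needed beyond those 6.3 already triggers. The six-week repeat and the three-month check lie outside the scheduled fasting-glucose visits, but 6.3 already calls for them.

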7.1. Hypotheses

Primary hypotheses:

- In pediatric nondiabetic patients with NAFLD, improvement in insulin resistance over 96 weeks of treatment with metformin will result in sustained reduction in serum alanine aminotransferase (ALT) compared to treatment with placebo
- In pediatric nondiabetic patients with NAFLD, improvement in oxidative stress status over 96 weeks of treatment with vitamin E will result in sustained reduction in serum ALT compared to treatment with placebo

Secondary hypotheses:

- Treatment with metformin or vitamin E will result in sustained reduction in serum AST and GGT compared to treatment with placebo
- Metformin and vitamin E are equally effective in achieving histologic improvement in nondiabetic children with NAFLD
- Levels of proinflammatory cytokines and serum markers for fibrosis will decrease with treatment with metformin and with vitamin E compared to treatment with placebo
- Pediatric nondiabetic patients with NAFLD have an impaired quality of life, and these scores will improve as their serum ALT improves upon treatment with metformin or vitamin E compared to treatment with placebo

Other questions to be addressed:

- We predict that insulin resistance is common in pediatric nondiabetic patients with NAFLD and will be significantly related to waist-to-hip ratio, waist circumference, serum ALT, and hepatic histology
- We predict that degree of obesity will be significantly related to hepatic histology in pediatric nondiabetic patients with NAFLD and more severe obesity (BMI or BMI z score) will be related to greater elevations in ALT and more advanced hepatic histology

- We predict that serum markers for steatosis, inflammation, and fibrosis will be significantly related to hepatic histology in pediatric nondiabetic patients with NAFLD
- We predict that worsening hepatic histology will be significantly related to a worsening in health-related quality of life in pediatric nondiabetic patients with NAFLD and more advanced histology will have worse health-related quality of life as measured by scores on the PedsQL
- We predict that improvement in the measures of insulin resistance will be significantly related to improvements in liver histology, serum ALT, and serum markers for steatosis, inflammation, and fibrosis in pediatric nondiabetic patients with NAFLD
- We predict that therapy with vitamin E will improve insulin resistance in pediatric nondiabetic patients with NAFLD
- We predict that improvement in liver histology upon treatment with insulin sensitizers will be significantly related to improvements in waist-to-hip ratio and waist circumference in pediatric nondiabetic patients with NAFLD
- We predict that therapy with same dose metformin across different age, height, and weight groups will have similar weight loss effects in pediatric nondiabetic patients with NAFLD
- We predict that maturation and growth (Tanner staging, anthropometric measures) will be similar across treatment groups in pediatric nondiabetic patients with NAFLD

7.2. Outcome measures

The primary outcome measure is the reduction in serum ALT after 96 weeks of treatment to either 50% of the baseline value OR to 40 U/L or lower which is sustained for at least one year. Other outcome measures are as follows:

- Reduction in serum aspartate transferase (AST) after 96 weeks of treatment to either 50% of the baseline value OR 40 U/L or lower which is sustained for at least one year.
- Reduction in serum gamma glutamyl transferase (GGT) after 96 weeks of treatment to either 50% of the baseline value OR 40 U/L or lower which is sustained for at least one year.

- Change in anthropometric measurements (weight, BMI, BMI z score, waist-to-hip ratio, waist circumference, triceps skin fold thickness and total body fat) after 96 weeks of treatment compared to baseline.
- Change in Tanner staging after 96 weeks of treatment compared to baseline.
- Change in insulin resistance (assessed by HOMA), serum vitamin E levels, cytokines, fibrosis markers, and lipid profile after 96 weeks of treatment compared to baseline.
- Change in health-related quality of life (PedsQL) after 96 weeks of treatment compared to baseline.

The histologic outcome measures require improvement in NAFLD activity after 96 weeks of treatment as determined by liver biopsies pre- and post-treatment. The histologic measures are derived from changes from baseline to the end of treatment in the NASH CRN NAFLD/NASH activity score (NAS). The NAS ranges from 0 to 8 (highest activity) and is calculated as the sum of three components of the standardized histologic feature scoring system for liver biopsies:

$$\text{NAS} = \text{Steatosis score (0-3)} + \text{Lobular inflammation score (0-3)} + \text{Hepatocyte ballooning score (0-2)}$$

Outcome measures derived from the NAS will include, but not be limited to:

- Change in NAS after 96 weeks of treatment compared to baseline NAS
- Changes in fibrosis, steatosis, lobular inflammation, hepatocyte ballooning and other specific feature scores from the histologic scoring system after 96 weeks of treatment compared to baseline
- Improvement in NAS and in specific features defined as any improvement in the corresponding scores

7.3. Statistical analysis

Primary hypotheses:

Statistical analyses for the two primary hypotheses will follow the intention-to-treat paradigm, which means that all randomized patients with baseline and 96 week serum ALT values will be analyzed in the treatment group to which they were assigned. Any randomized patient who does not have the requisite ALT values will be accounted for and compared by assigned treatment group. Patients not able to be included in the intention-to-treat analyses will be compared to those who are included with respect to demographic and other characteristics.

Since the primary outcome measure, defined in Section 7.2, is a binary indicator of sustained reduction in ALT after 96 weeks of treatment compared to baseline and since the randomization is stratified by clinic, P-values for the primary hypotheses will be derived from the Mantel-Haenszel χ^2 test for stratified 2x2 tables⁴⁴. Two P-values will be derived: one comparing proportions improved in the group assigned to metformin compared to the group assigned to placebo and another comparing the group assigned to vitamin E to the group assigned to placebo. Since two primary comparisons are planned, a P-value of 0.025 will be considered significant, applying a Bonferroni correction for multiple comparisons.

Given the randomized design and adequate size planned for the TONIC trial, it is unlikely that confounding of the treatment groups by covariates related to the change in serum ALT will occur. However, if confounding should occur, logistic regression analyses with sustained reduction in ALT as the binary response and treatment group indicators and any suspected confounders as covariates will be carried out to determine the sensitivity of the primary P-values to confounding.

Secondary hypotheses:

Statistical analyses for the first secondary hypothesis, that treatment with metformin or vitamin E will result in sustained reduction in serum AST and GGT compared to treatment with placebo, will be the same as described for primary hypotheses.

The second secondary hypothesis, that metformin and vitamin E are equally effective in achieving histologic improvement in nondiabetic children with NAFLD, involves the histologic outcome measure. Equivalence will be assessed by means of 95% confidence intervals on the difference in proportions improved.

Analyses for outcomes related to other secondary hypotheses will be conducted in two ways. Improvement will be analyzed both as a binary outcome (improved vs. not improved) and also in terms of the numerical change in the outcome. Binary outcomes will be compared using the Mantel-Haenszel χ^2 test for stratified 2x2 tables. Numerical changes will be analyzed by descriptively comparing the between-treatment group differences in mean and median changes; P-values will be derived from Wilcoxon rank sum tests for comparison of the distribution of changes in each group. If concerns about confounding arise, logistic regression models for improvement outcomes and linear regression models for numerical change outcomes will be used to correct for the confounding. Analyses for secondary hypotheses will generally involve three separate analyses, one for each treatment group comparison: metformin vs. placebo, vitamin E vs. placebo, and metformin vs. vitamin E. No adjustments for multiple comparisons will be applied to the secondary hypotheses; however, any significant findings must be interpreted taking into account the strength of the finding and its biologic plausibility.

Other questions to be addressed:

A series of other questions of interest were listed in Section 7.1. Analyses related to these questions will involve a mix of appropriate exploratory and confirmatory analyses, similar, but not limited to those described for the primary and secondary hypotheses.

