7.4. Missing data

The occurrence of missing data in TONIC trial is expected to be low and, when present, is expected to be equally distributed across the 3 treatment groups. We estimate that careful selection of patients during the 16 weeks screening phase and the consent process should result in no more than 10% missing data from patients who drop out before completing the 96 week treatment period. In primary, intention-to-treat analyses, patients with missing data will be considered unimproved on the primary outcome measure.

The proportions with missing data will be compared across treatment groups using χ^2 tests. If the amount of missing data exceeds 10% and the frequency of missing data differs by treatment group, then a variety of sensitivity analyses will be carried out to compare with the primary analysis using all available non-missing data: (1) compare pessimistic and optimistic imputations of the missing values, (2) correct for missing data using multiple imputation with 10 replicated samples, and (3) use mixed random effects logistic or linear regression models, depending on the type of outcome measure.

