7.5. Justification of sample size

The planned sample size for the TONIC trial is 180 patients with equal allocation to each of the three treatment groups (60 per group).

We based the sample size estimates on a two-group, binomial comparison of the proportions of patients satisfying the primary outcome, reduction in serum ALT to either 50% of the baseline value OR to 40 U/L or lower which is sustained for at least one year (defined in Section 7.2) over the 96 week course of treatment. Since TONIC is a three group trial with two primary hypotheses, we assume that the two primary comparisons, metformin vs. placebo and vitamin E vs. placebo, require the same sample size and reduce the type I error from 0.05 to 0.025 (Bonferroni correction). Expected proportions improved were approximated using pilot data from a 48-week metformin study ([name], personal communication) and from a consensus among our investigators as to the response in the placebo group. Currently, there are no available data to estimate the response in vitamin E, which is assumed, for purposes of planning the trial, to be the same as for metformin.

The sample size calculations were performed using the PS⁴⁵ software using the formula:

$$n = \frac{\left[z_{1-\alpha/2} \sqrt{2\bar{\pi}(1-\bar{\pi})} + z_{1-\beta} \sqrt{\pi_1(1-\pi_1) + \pi_2(1-\pi_2)} \right]^2}{(\pi_1 - \pi_2)^2}$$

where,

n = sample size per group

π_1 = expected proportion improved in placebo group (assumed=0.20)

π_2 = expected proportion improved in metformin or vitamin E group (0.50)

$\bar{\pi}$ = average of π_1 and π_2

α = Two-sided type I error (0.025, Bonferroni corrected for two comparisons)

β = Type II error (0.10; ie, 90% power)

The number per group, using the above formula is 60 patients; or a total of 180 for the trial. As indicated in Section 7.4, patients with missing primary outcome data will be considered unimproved and will be included in the 180 patients.

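### Section 7.3 limits the primary analysis to patients with baseline and week-96 ALT, while Sections 7.4 and 7.5 count patients with missing outcomes as unimproved; the plan does not say which rule governs

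*Supplement*

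**What the plan says.** Section 7.3 says that the two primary hypotheses follow intention-to-treat and explains the term: "all randomized patients with baseline and 96 week serum ALT values will be analyzed in the treatment group to which they were assigned". It then treats the remaining randomized patients as outside the analysis: "Patients not able to be included in the intention-to-treat analyses will be compared to those who are included" on demographic and other characteristics.

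Section 7.4 gives a scoring rule: "In primary, intention-to-treat analyses, patients with missing data will be considered unimproved on the primary outcome measure". Section 7.5 refers back to it when justifying the sample size: "patients with missing primary outcome data will be considered unimproved and will be included in the 180 patients".

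The second paragraph of Section 7.4 makes sensitivity analyses conditional on missing data exceeding 10% and differing by group. Their purpose is "to compare with the primary analysis using all available non-missing data".

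The synopsis says only that all analyses are by intention-to-treat. The document history records January 2006 changes to Sections 7.4 and 7.5, and no change to Section 7.3 in any version.

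**The concern.** One label, intention-to-treat, is attached to two denominators. Under Sections 7.4 and 7.5 no randomized patient is left out, so the sentence in Section 7.3 about patients who cannot be included would describe nobody. Under Section 7.3 those patients exist and are excluded, so the scoring rule in Section 7.4 would have nobody to score. Both cannot describe the primary analysis.

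At stake are the denominators and P-values of both primary comparisons. The AST and GGT analyses inherit the problem, because Section 7.3 says they follow the primary method. So does the interim efficacy look in Section 7.6, which uses the primary outcome. A completer analysis is also exposed to selection if the reasons for a missing week-96 ALT differ by arm.

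**Working it through.** **Inputs from the plan.** 60 per group; expected response 20% (placebo) and 50% (active); two-sided alpha 0.025 per comparison; 90% power (Section 7.5). The test is the Mantel-Haenszel chi-square stratified by clinic (Section 7.3). Section 7.4 expects "no more than 10% missing data from patients who drop out before completing the 96 week treatment period", equally spread over the groups.

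**Assumptions added here.** The plan gives no per-clinic data, so clinics are collapsed to one stratum, without continuity correction. Responder counts and the split of missing patients are illustrative.

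**Step 1: the plan's own figure.** With π̄ = 0.35, the formula in Section 7.5 gives
n = [2.2414·√(2·0.35·0.65) + 1.2816·√(0.20·0.80 + 0.50·0.50)]² / 0.30² = (1.5119 + 0.8206)² / 0.09 = 60.45.
The stated 60 per group is reproduced to within rounding; power at 60 is 89.8%.

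**Step 2: both rules on the same data.** For active responders a of n₁, placebo responders c of n₂, N = n₁+n₂ and m = a+c:
E = n₁m/N; V = n₁n₂m(N−m)/[N²(N−1)]; χ² = (a−E)²/V on 1 df.

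| Missing active / placebo | Responders active / placebo | Section 7.3 (completers) | Sections 7.4/7.5 (missing = unimproved) |
|---|---|---|---|
| 9 / 3 | 22 / 12 | 22/51 v 12/57: E=16.06, V=5.86, χ²=6.03, P=0.014 | 22/60 v 12/60: E=17, V=6.14, χ²=4.07, P=0.044 |
| 3 / 9 | 24 / 12 | 24/57 v 12/51: E=19, V=6.04, χ²=4.14, P=0.042 | 24/60 v 12/60: E=18, V=6.35, χ²=5.67, P=0.017 |
| 6 / 6 | 23 / 12 | 23/54 v 12/54: χ²=5.07, P=0.024 | 23/60 v 12/60: χ²=4.84, P=0.028 |

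Each row has 12 of 120 missing, that is 10%. Rows 1 and 2 flip in opposite directions, so neither rule is always the stricter. Row 3 flips only because both P-values lie close to 0.025. Flips of this kind also occur with a continuity correction.

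**Step 3: how often the verdicts differ.** Simulation, 400,000 trials per scenario, each patient missing with the stated probability:

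| Missing placebo / active | 20% v 50% | 20% v 40% |
|---|---|---|
| 10% / 10% | 4.7% | 7.1% |
| 5% / 15% | 14.7% | 17.3% |
| 15% / 5% | 6.6% | 12.9% |

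**Step 4: would the safeguard in Section 7.4 catch it?** Take row 1 and assume 6 missing in the third arm. The total is 18/180 = 10%, which does not exceed 10%. The three-group chi-square is 3.33 on 2 df, P=0.19. Taking 0.05 as the threshold for a difference, neither trigger is met, and no sensitivity analysis would be required.

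**Step 5: cost of the missing-as-unimproved rule.** Let 20% and 50% be rates among patients with data, with 10% missing in each arm. The expected rates become 0.9·0.20 = 18% and 0.9·0.50 = 45%, a difference of 27 points instead of 30. Power at 60 per arm is Φ[(0.27·√60 − 2.2414·√(2·0.315·0.685)) / √(0.18·0.82 + 0.45·0.55)] = Φ(0.985) = 83.8%. A completer analysis at 54 per arm has 86.0%. Reaching 90% under the missing-as-unimproved rule would need 72 per arm.

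**The case against.** The strongest reply is that only one sentence in the plan says how a patient with missing data is scored in the primary test. It is in Section 7.4, and Section 7.5 repeats it with a cross-reference. The document history shows Section 7.5 being aligned with it in January 2006, while Section 7.3 is not listed as edited. The likeliest explanation is a passage that was never harmonised. This stands as to intent. It does not remove the conflict: Section 7.3 is current text and no clause ranks the sections.

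A reader might take the words in Section 7.4 about non-missing data as a second declaration that the primary analysis is a completer analysis. The grammar does not settle that, because the phrase may equally describe the sensitivity analyses. It adds ambiguity and proves nothing alone.

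A reader might also infer that metformin patients will be missing more often, because Section 6.1 reports gastrointestinal effects in as many as 30%. That figure counts symptoms, not missing ALT. The plan titrates the dose and allows reduction, the paediatric pilot described in Section 3.3.1 had no gastrointestinal drop-outs, and patients taken off drug are still followed (Sections 6.1 and 6.3). The documents give no basis for predicting the direction of any imbalance.

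Finally, a more dramatic flip can be built from 12 v 3 missing (20% v 5%), but that departs from the plan's expectation of at most 10%, equally distributed. With 6 missing in the third arm it would also trigger the sensitivity analyses (21/180 = 11.7%; three-group P=0.033). The examples above keep to 10% overall, although the first two still depart from equal distribution.

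**Conclusion.** The contradiction is real and needs correcting: the primary denominator is defined in two incompatible ways in the current text. Sections 7.4 and 7.5 very probably carry the intended rule, so it would be too strong to say that the trial has two primary analyses of equal standing. The remaining wording in Section 7.3 still lets an analyst follow either rule and claim compliance.

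Under the plan's own assumptions (20% v 50%, 10% missing in each arm), the verdicts differ in about 1 trial in 20, and with equal missing counts only for borderline results. With 5% missing on placebo and 15% on active treatment it is about 1 in 7. Differing verdicts here means significant against not significant at 0.025; no reversal in the direction of effect is shown. These figures rest on collapsed clinics and illustrative missing patterns.

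**What to change.** - **Section 7.3, definition:** state that all 180 randomized patients are analysed in their assigned group, and that any patient whose primary outcome cannot be determined is counted as unimproved.
- **Section 7.3, following sentences:** reword, do not delete. For example: patients with missing ALT values will be compared with those with complete values by treatment group and baseline characteristics. The comparison is useful; only the implication that these patients leave the primary analysis is wrong.
- **Section 7.4:** name the analysis of non-missing data as a completer sensitivity analysis, so that it cannot be read as the primary one.

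The change takes a few sentences and needs no new data or visits. The statistical cost should be stated in Section 7.5: at 10% missing in each arm, a 27-point instead of a 30-point expected difference and about 84% instead of 90% power at 60 per group. That cost applies if 20% and 50% are rates among patients with data. If they were meant to include missing patients as unimproved already, Section 7.5 should say so, and the 90% stands.
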